9. RESEARCH METHODS

9.1 STUDY DESIGN

This is an observational cohort study based on existing data.

BOEHRINGER INGELHEIM Group of Companies**NIS Protocol Template****Study number: 1484.0014****Page 12 of 30****Document number: <insert>****9.1.1 Study population**

Study inclusion criteria: All patients ≥ 50 years, with a GA diagnosis in at least one eye, including in the [REDACTED] database identified during the study period (January 2015 to April 2023).

Exclusion criteria: Patients without the information of laterality will be excluded.

No other exclusion criteria are applied for the identification of the study population and description of the patients and eye at baseline.

Additional note:

For certain analysis the patient population will be restricted to those with at least 12, 24, 36, 48, or 60 months of history following diagnosis of GA. For the analysis requiring a VA reading, a restriction to those patients with valid VA readings at the index diagnosis and the respective follow-up times will be applied.

For analysis estimating the size of the GA population relative to other retinal diseases, the same timeframe requirements that the study population will be applied. In this population, any patient in the database will be eligible, and the diagnosis of DME, DR or other conditions may be used for subgroup comparisons.

Primary Disease Definitions

In the [REDACTED] Database, retinal and other diseases are identified using the International Classification of Diseases (ICD), Tenth Revision, Clinical Modification. ICD 10 codes were launched in the USA in October 2015, and are the only version of ICD codes with adequate descriptions of GA and dry AMD severity. As such, only ICD 10 codes will be analyzed in this study and the study period defined above is directly related to the launch of ICD 10 plus a small buffer allowing for physician familiarity.

These codes are entered by the physician at patient visit, with an associated laterality. This, along with the ICD 10 laterality is used in combination to confirm in which eye the disease is occurring. For this study, a patient eye will be considered to have the study disease so long as there is an accompanying ICD code. The primary study diseases to be analyzed are dry AMD, GA and wAMD, and will be identified using the ICD codes in Table 1 below.

Table 1. Study disease definitions-codes.

Study Disease Definitions			
	Dry AMD*	Dry AMD with GA*	wAMD*

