Prevalent visit – all visits following the incident visit in patient eye history while identified with GA in the [REDACTED] database. Prevalent visits may occur year after year throughout the patients' journey.

Study period

Patients will be identified from January, 2015 to April, 2023.

Selection period: Eligible patients must have at least one GA diagnosis between October 2015 and April 2023. The date of the first GA diagnosis will be considered as index date. For all follow up analysis, eligible patient eyes should be divided in those with at least 12, 24, 36, 48 and 60+ months of follow up. follow up requires multiple visits spanning over the outlined durations and total follow up is defined as the time between incident diagnosis and the final visit in the dataset.

BOEHRINGER INGELHEIM Group of Companies**NIS Protocol Template****Page 14 of 30****Study number: 1484.0014****Document number: <insert>**

Follow-up period: up to 60-month period following the index diagnosis date of GA (exploratory follow-up of 1, 2, 3, 4, 5 years may be run as cutoff points)

Pre-selection period: January 2015-September 2015. This period will be used to identify patients who have dry AMD using ICD9 coding, and will help to assign patients into the incidence or prevalence status.

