9.3 VARIABLES

9.3.1 Exposures

Study Treatments

The treatment variables below are identified at the patient eye level and will be used to describe the treatment patterns throughout the analysis. These treatment variables will be analyzed throughout the entire study period. Each treatment type can only occur once per patient eye visit and will be identified at every distinct visit where the following codes are present. Treatment must contain both the Current Procedural Terminology (CPT) codes for intravitreal injection and the J-codes specifying the study treatment (Table 2).

Though not common, it is possible for multiple different treatment types to occur on the same day, in which case both treatments would be captured for analysis i.e., a patient could get a laser and an injection at the same visit.

Table 2. Study Treatment Definitions

Study Treatment Definitions		
Treatment	CPT Code	
		[REDACTED]
		[REDACTED], C9214, C9257, Q9977
		Eylea- J0178, C9291, Q2046
		Lucentis-J2778, C9233
		Beovu- J0179

BOEHRINGER INGELHEIM Group of Companies

NIS Protocol Template

Study number: 1484.0014

Page 16 of 30

Document number: <insert>

		Susvimo – C9093, J2779 Byooviz- Q5124 Vabysmo- J2777, C9097 Cimerli- C9097, Q5128
Corticosteroids	Intravitreal Injection – 67028	Ozurdex-J7312 Triamcinolone-J3300, J3301 Iluvien-J7313 Yutiq-J7314
Laser	Focal Grid Laser- 67210 Panretinal Photocoagulation- 67228	Not Applicable
C3 Inhibitor	[REDACTED]	J3490, C9399

[REDACTED] will also accept an incoming procedure medication that is associated to an [REDACTED]
[REDACTED]
[REDACTED]

9.3.2 **Outcomes**9.3.2.1 Primary outcomes

- [REDACTED]

This study will evaluate the disease progression over time. The main progression endpoints will be for the study eye, [REDACTED], changes in the GA lesion location, changes in the VA or changes in the size of the GA lesion. For the fellow eye the progression endpoints will also include the developing of GA.

*Please see Table 1, that includes the disease definitions (dry AMD, GA, and wAMD) based on ICD codes.

- **Position of GA lesion will be assessed over time.** The position of GA lesion will be defined using ICD 10 coding defined below. Any change in location status will be identified as progression of GA

Study Disease Definitions-lesion location		
	GA without Subfoveal Involvement	GA with Subfoveal Involvement
ICD 10	H35.3113, H35.3123, H35.3133, H35.3193,	H35.3114, H35.3124, H35.3134, H35.3194

BOEHRINGER INGELHEIM Group of Companies

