9.4 DATA SOURCES

Founded in 2014, [REDACTED] is the first-to-market EHR data analytics provider in the retina space. [REDACTED] was founded by practicing retina specialists and data-analytics experts with the mission to provide real-world insights from analyzing retina practices' electronic health data. [REDACTED] database consists of de-identified data from EHRs from a geographically diverse panel of United States based private retina specialists. All data comes exclusively from private retina clinics; [REDACTED] not collect data from hospitals or institutions. [REDACTED]

[REDACTED] by an anonymized patient code assigned by the software vendor. Data from multiple sources are organized into the structured database residing in US-based cloud servers. Data is maintained in a secure, password-protected environment using standards associated with personal health information (PHI).

Data Completeness

The Electronic Medical or Health Record represents the entire patient file as maintained by the treating physician and practice with the exception of diagnostic images. Records are continuous regardless of the physician in the practice treating the patient but only to the extent the patient is treated in the same practice. The file is therefore a complete record of the treatments rendered through the practice.

Data completeness within an EHR is entirely dependent on the treating physician recording diagnostic, treatment and other information. Completion rates vary by data element and depend on the treating physician's opinion of the future utility of the information related to that patient's clinical presentation. Crucial visit information such as Procedures, drugs administered, diagnoses, payer, are required at every visit. Outcomes such as IOP and Visual Acuity are entered at 95+% of visits. Foveal thickness is recorded in approximately 30% of encounters where an OCT scan was taken. [REDACTED] neither adds nor removes information received. [REDACTED] receives the key treatment and outcomes information but does not receive every field contained in an EHR. [REDACTED] does extensive work with physicians analyzing their own data through clinical trials or other projects and have not found inconsistencies between the data and the physician's expectation of the data. This iterative process is an integral step in ensuring data accuracy and completeness of our data.

Capture of Concomitant Medications/Exposure

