9.7 DATA ANALYSIS

9.7.1 Main analysis

All analysis will be performed individually on the study population(s). All study results will be provided in tables, and key findings will be highlighted and summarized. The analyses will be conducted at both the patient and patient eye level, as appropriate.

Analysis for objective:

To describe the characteristics* of patients with GA in at least one eye.

To describe characteristics* of the study eye and the fellow eye, at index diagnosis (i.e., proportion of patients with GA in the fellow eye, [REDACTED]

All demographics, and clinical characteristics will be summarized at the index diagnosis date (first diagnosis of GA in the study eye).

Characteristics include demographics, comorbidities, comedications (patient level).

And at eye level; AMD, GA, eCNV, other ocular comorbidities, functional parameters i.e. VA. As well as treatments administered prior to or at index.

Summary will include descriptive statistics; continuous variables will consist of mean (SD) and median (IQR) while categorical variables will be described using frequency and proportion. Absolute numbers (n) of the variables (either yes or patients as appropriate) will be always included in the description of the results.

Analysis for objective:

To evaluate and characterize the progression of newly diagnosed patients with GA during a 5-year follow-up period. To describe patients' characteristics, study eye and the fellow eye characteristics, [REDACTED]

[REDACTED] or progression of the GA lesion in the study eye. To evaluate changes in VA, to evaluate changes in the lesion location, and lesion size (where available).

Patients with GA will be analyzed as an overall group. Subgroups will be also analyzed separately: only GA, GA and wAMD, GA and other comorbidities, and bilateral GA at baseline.

Ocular comorbidities will also be tracked longitudinally (yearly) from index date (GA diagnosis in the database) to better understand the disease journey.

Disease progression will be analyzed at both patient and each individual eye level.

Progression to dry AMD, to GA and to wAMD will be assessed independently using time to event analysis, and also the rate of progression that is seen in the study (2nd, 3rd, 4th, and 5th) years. Bilateral GA eyes at baseline will be evaluated for progression to wAMD

BOEHRINGER INGELHEIM Group of Companies**NIS Protocol Template****Study number: 1484.0014****Page 23 of 30****Document number: <insert>**

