9.9 LIMITATIONS OF THE RESEARCH METHODS

As with real world data entered during patient encounters, there are limitations due to the entry process and general operations of both physicians and clinics. The [REDACTED] database includes only data from visits that occurred at the practices contributing to the database. Anything occurring during visits to a retina specialist/ophthalmologist in a different practice, state, country etc. is not captured.

[REDACTED] does receive information on previous history, referrals, etc. from overall patient history fields in attempt to gain insights on potential previous physicians, however [REDACTED] completely relies upon the physician to enter these data. This is a limitation of the study regarding the incidence and prevalence of the study diseases.

Retinal specialists are the primary specialty that will observe and treat all forms of AMD. However, there is a portion of mild dry AMD patients who are being observed by their general ophthalmologist. As this study will focus on GA specifically, there should not be a concern with underrepresentation in the database, as it is the most severe form of dry AMD. Out of the 1.6 million eyes with 1+ visit to in the [REDACTED] in 2022, dry AMD was the most prominent disease with ~180,000 eyes, twice as large as those with wAMD. While this study will identify newly diagnosed cases of GA and wAMD, there is a possibility that a patient was diagnosed prior by an ophthalmologist or other retina specialist. As these are severe versions of AMD that are handled only by retina specialists in the USA, it is a limitation that must be addressed.

Prevalent cases are less affected as per the study definitions they are being seen over a multiple year span in the same dataset. While it is possible, they are seeing other healthcare

BOEHRINGER INGELHEIM Group of Companies**NIS Protocol Template****Study number: 1484.0014****Page 27 of 30****Document number: <insert>**

professionals during this time frame, they are continuing to visit their retina specialist for follow up. Patients who leave the panel for any number of reasons (death, moving, poor experience) are only able to be identified as lost to follow up. No other claim can be made on these cases, and for the study purposes they would no longer be included in any analysis from that point onwards.

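### The share of eyes treated before index is taken over all eyes with no look-back requirement, so it can only be understated, by an amount the plan does not measure

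*Combined protocol and SAP*

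**What the plan says.** - **Baseline table.** Describing the study eye and the fellow eye at index is a primary objective (Section 8). Section 9.7.1 ends its list of eye-level characteristics with "As well as treatments administered prior to or at index". Categorical items are summarised by frequency and proportion. No look-back length is given.
- **Index and eligibility.** Under the study period heading in Section 9.1.1, "The date of the first GA diagnosis will be considered as index date". Missing laterality is the only exclusion, and "No other exclusion criteria are applied for the identification of the study population and description of the patients and eye at baseline".
- **How treatment is found.** For injections, Section 9.3.1 says "Treatment must contain both the Current Procedural Terminology (CPT) codes for intravitreal injection and the J-codes specifying the study treatment". It adds that "These treatment variables will be analyzed throughout the entire study period", so no fixed window before index is set.
- **Reach of the record.** Section 9.4 says records are continuous "only to the extent the patient is treated in the same practice", and concludes that "The file is therefore a complete record of the treatments rendered through the practice". Section 9.2.1 dates physician coverage from 2015. Section 9.9 states that care in other practices is not captured and, for newly diagnosed GA and wAMD, that "there is a possibility that a patient was diagnosed prior by an ophthalmologist or other retina specialist".

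**The concern.** Index is the first GA code in the database. For a referred patient, that visit may also be the first visit of any kind. Such an eye has no recorded time before index in which a treatment could appear, whatever was done elsewhere. If it is tabulated with the other eyes, an absence of observation becomes an absence of treatment.

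The rationale in Section 7 concerns wAMD in the study and fellow eyes of patients with GA, together with treatment patterns. The share of eyes already treated when GA is first recorded belongs to that picture and sits in a primary-objective table. As planned, it would depend partly on how long each practice had known the patient, and a reader of the table could not see this.

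**Working it through.** **1. No figure to reproduce.** The documents give no prior-treatment proportion, no count of eyes whose first visit is the index visit, and no distribution of history before index. The check traces the rules and then illustrates size.

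**2. Follow one eye.** It is treated in practice A, moves to contributing practice B, and receives a GA code at its first visit there.
- It is eligible, because no earlier visit is required.
- Index is that first visit.
- Treatment given at that visit is captured as treatment at index.
- Earlier treatment in practice A lies outside the record that Section 9.4 describes.
- Nothing takes the eye out of the denominator.

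**3. Look for a correction elsewhere.**
- The January to September 2015 pre-selection period identifies dry AMD and helps assign incident or prevalent status. It is not assigned to prior treatment.
- Section 9.9 mentions physician-entered history fields, but ties their limitation to incidence and prevalence. The visible text of Section 9.3.1 does not use them to find treatment.
- Section 9.3.3.3 gives smoking and alcohol an unknown level. Prior treatment has none.

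**4. Size of the shortfall.** Let f be the share of eyes with no visit before index, p1 the true prior-treatment rate in eyes with earlier visits (taken here as fully captured), and p0 the true rate in eyes without.

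- True share: T = (1 − f) × p1 + f × p0
- Observed share: O = (1 − f) × p1
- Shortfall: T − O = f × p0, which is never negative and, for f above zero, is zero only when p0 = 0

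All values of f, p0 and p1 below are assumptions.

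| p1 | p0 | f | True T | Observed O | Shortfall (points) |
|---|---|---|---|---|---|
| 25% | 25% | 30% | 25.0% | 17.5% | 7.5 |
| 25% | 25% | 60% | 25.0% | 10.0% | 15.0 |
| 20% | 0% | 30% | 14.0% | 14.0% | 0.0 |
| 20% | 5% | 30% | 15.5% | 14.0% | 1.5 |
| 20% | 10% | 30% | 17.0% | 14.0% | 3.0 |
| 20% | 30% | 30% | 23.0% | 14.0% | 9.0 |

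For scale only, Section 9.5 counts 113,408 GA eyes. Then 0.075 × 113,408 ≈ 8,506 and 0.15 × 113,408 ≈ 17,011 eyes. The baseline table has study and fellow eyes as its units, so these are not its exact denominators.

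**5. Restriction alone is not a cure.** A summary limited to eyes with earlier visits returns p1. In the last four rows that is 20%, against true all-eye values of 14.0%, 15.5%, 17.0% and 23.0%. It equals the all-eye value only when p0 = p1.

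**6. Short histories.** If records start in January 2015, the longest possible look-back is about 9 months for an October 2015 index and about 99 months (8 years and 3 months) for April 2023. Eyes with a short but non-zero look-back can also lose earlier treatment, so f × p0 is a lower bound on the total shortfall.

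**The case against.** The data gap is disclosed. Sections 9.4 and 9.9 say that the record covers one practice and that outside care is missed. That stands; what is absent is the consequence for this row and a rule for handling it.

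Ascertainment may also be wider than the code rule suggests. After Table 2, a partly redacted sentence in Section 9.3.1 accepts an incoming procedure medication, and Section 9.2.1 mentions patient-provided information and text mining of notes. The visible text does not tie either to treatment in other practices, but the redaction and the codes file named in Annex 1, which was not available, keep the conclusion to the visible text. Nor does the plan say that unobserved treatment is tabulated as none. That is inferred from the missing unknown level.

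The row is also not the only evidence on existing wAMD. Diagnoses come from ICD codes, which can be entered at the index visit itself, and the anti-VEGF question on the title page concerns progression. This lowers the stakes.

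A reader might infer three stronger points that the documents do not support:
- **First-visit eyes count as never treated.** They do not: treatment at index is included in the variable.
- **Diabetes has the same defect.** Section 9.3.3.2 also uses the drugs a patient is taking, and Section 9.9 names the medication list as the workaround, so diabetes can be found at a first visit.
- **Later group comparisons are distorted.** Section 9.7.1 takes those characteristics at the time of assignment to the group, not only at index, and no such effect has been shown.

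**Conclusion.** The point holds for one quantity: the all-eye proportion treated before index. On the visible text this gap can push it only downward, by at least f × p0. With an assumed p0 of 25%, that is 7.5 points at f = 30% and 15 points at f = 60%; if no first-visit eye was treated earlier, the term is zero. The conclusion assumes that eyes without an earlier visit stay in the denominator as untreated, and that no redacted route recovers outside treatment.

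A reader might go further and take the observed figure as the true figure times (1 − f). That holds only if eyes with and without earlier visits have the same prior-treatment rate, for which the documents give no basis. The actual size cannot be derived from the documents, although the sponsor can count f directly. This is a cheap improvement to a primary-objective table, and it does not by itself call the progression analyses into question.

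**What to change.** In Section 9.7.1, under the analysis of characteristics at index:

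1. Derive look-back for each eye, from first database visit to index, and tabulate its distribution, including the share of eyes with none.
2. Report treatment at index and treatment before index as separate rows. Label the second as recorded in the practice before index.
3. Show eyes with no earlier visit as not observed, not as untreated.
4. Keep the all-eye figure. Beside it, report the proportion among eyes with a prespecified minimum history before index, for example 12 months.

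The cost is one derived variable, one extra category and one extra column, with no new data. The drawback is that the restricted group is already in retina care and may differ from first-visit eyes. It must be labelled as such and must not replace the all-eye summary. A 12-month minimum also does not establish whether an eye was ever treated.

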Data analysis:	
In this study, both patients and eyes will be considered as the analysis unit. Baseline characteristics will be summarized using descriptive statistics. For continuous variables, the mean, standard deviation, median and range will be presented. For categorical variables frequency and proportion will be used. Variables are identified and calculated at the index diagnosis and throughout the follow-up period for primary outcomes like VA.
 
In the progression analysis, the population will be restricted to patients with a minimum follow-up time (i.e. multiple visits at least one year apart, at least two years), or patients with valid VA reading at the index diagnosis and a second follow-up timepoint. [REDACTED]
 
The analysis of incident and prevalent calculations will use as the denominator, all patients referred to the retinal specialist. The proportion of patients with a GA diagnosis referred to the retinal specialist will be put into perspective by comparing to other conditions, such as proportion of patients referred to the retinal specialist with a diabetic macular edema (DME) diagnosis, or with a diabetic retinopathy (DR) diagnosis etc. Additionally, extrapolations will be done to approximate to a population-based estimate.
									
Milestones:	
 
 Start of data collection	05/2023		
 
 End of data collection	06/2023		
 
 Final report of study results	06/2023		
 
	Start of data collection	05/2023		End of data collection	06/2023		Final report of study results	06/2023	
Start of data collection	05/2023									
End of data collection	06/2023									
Final report of study results	06/2023									

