ICD 10	H35.311X, H35.312X, H35.313X, H35.319X	H35.3113, H35.3114, H35.3123, H35.3124, H35.3133, H35.3134, H35.3193, H35.3194	H35.321X, H35.322X, H35.323X, H35.329X
ICD 9 (2015 only)	362.51	N/A	362.52

*a comprehensive list of all AMD ICD codes is included in the Appendix

BOEHRINGER INGELHEIM Group of Companies**NIS Protocol Template****Study number: 1484.0014****Page 13 of 30****Document number: <insert>**

Patients could have simultaneously a diagnosis of wAMD and GA in the same eye. If both conditions are present, wAMD will be described as part of the comorbidities of the study or fellow eye. Patients could also have other ocular comorbidities affecting VA (section 9.3.3), those will be described and for the progression analysis will be analyzed separately.

For the follow-up analysis in the study eye or fellow eye, results will be described for all GA patients, patients with GA and wAMD, and patients with patients with GA only (without wAMD or other ocular comorbidities).

As the progression analysis tracking multiple different metrics across 2 eyes, it will be conducted at the patient level. Bilateral AMD disease is quite common (and will be identified), therefore the following methodology will be used to identify the 'Study' (primary) eye and the 'Fellow' (secondary) eye:

Study Eye – The first study eye in patient history identified with GA in the [REDACTED] database. GA is the only identifying disease in this case, and wAMD or dry AMD (without GA) in the study eye is not taken into account for study eye definition. If patients are bilaterally diagnosed, the study eye will be selected at random.

Fellow Eye – is defined as the other eye in a patient having their study eye diagnosed with GA. The fellow eye can have dry AMD, wAMD, GA or other retinal conditions. The fellow eye will be followed for progression purposes throughout the study.

Disease Status

Patient eyes will be identified at every visit throughout the study period to estimate the first time occurrence of GA and to estimate the proportion of patient with the disease over the years of the study period. Each visit will be classified as either an incident or a prevalent visit, defined below:

Incident visit – The first visit in patient eye history identified with GA in the [REDACTED] database. This timepoint also acts as each patients' index diagnosis. The incident visit may only occur once and contribute to one calendar year.

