9.6 DATA MANAGEMENT

[REDACTED] extracts data weekly from various EHR vendors where it is then stored on secure servers accessible only to [REDACTED]. [REDACTED] has multiple data warehouses where an iterative standardization is applied to the data to combine different sources and ensure data accuracy.

Once all data cleansing and standardizing has been performed by [REDACTED], a static dataset is created specifically for the study to ensure there will be no variation in data for its duration. At this point, data accessible for analysis through Microsoft SQL Server Management Studio 18 and the building of the patient population begins. Only after the study population is completed, and all metrics relevant to the analysis have been identified and extracted in aggregated form to excel for further analysis and output generation. The statistical software used for this analysis will be R – version 3.6.3, which will be used for any statistical analysis

BOEHRINGER INGELHEIM Group of Companies**NIS Protocol Template****Study number: 1484.0014****Page 22 of 30****Document number: <insert>**

performed (t-tests, chi-square test or proportion, Confidence intervals etc.). Graphs and tables will be generated using both R and Excel, where applicable.

No personal data will be provided to Boehringer Ingelheim

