An additional analysis will be made to extrapolate the prevalent results to a national – US-level. For that analysis, the prevalence of GA will be considering all patients seen by a retina specialist in the given year. With this metric, estimation on a national level will be done using an estimation of all practicing US retina specialists.

When analyzing the rate of progression from dry AMD to GA, a conversion analysis will be done. This will include the overall rate of dry AMD eyes developing GA, along with a Kaplan Meier analysis assessing the rate of conversion over time. This analysis will track progression by month from diagnosis, censor any patient at the final visit in the database, and identify the incident GA diagnosis as an event.

Analysis for objectives:

To evaluate patients' management (i.e. patients visits and procedures) over the study period.

BOEHRINGER INGELHEIM Group of Companies**NIS Protocol Template****Page 24 of 30****Study number: 1484.0014****Document number: <insert>****Patients' management**

All visits, treatment, checkups, procedures, and other will be summarized across the duration of the study time frame as well as between the index diagnosis and at the 12 (24, 36, 48, 60) month follow up period.

An additional sub analysis will be conducted to evaluate the changes in the frequency of patients visits or procedures, checkups, after the third quarter of 2021 and after [REDACTED].

Summary will include descriptive statistics; continuous variables will be described by absolute numbers, the mean (SD), median and range, while categorical variables will be described using frequency and proportion. Absolute numbers (n), and correspondent percentage (%) of the variables (either eyes or patients as appropriate) will be always included in the description of the results.

Analysis for objective:

To describe and compare patients' characteristics in different progression subgroups (i.e. those that develop eCNV/those that not), of the overall GA population.

The following groups will be evaluated to better understand progression:

1. Patients that [REDACTED]

vs. those that do not in the 1, 2, 3, 4 and 5 years of follow up period.

2. Patients that [REDACTED]

vs. those that do not in the 1, 2, 3, 4 and 5 years of follow up period.

3. Patients with subfoveal lesion location vs. those with extrafoveal lesion location.

For this subgroup of patient's characteristics will be described and compared.

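### Where eyes are pooled, the plan names no allowance for two eyes from one patient, and it gives conflicting units for the progression analysis

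*Combined protocol and SAP*

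**What the plan says.** The plan gives more than one answer on the unit of analysis.

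- Abstract, data analysis entry: "In this study, both patients and eyes will be considered as the analysis unit".
- Section 9.1.1, on the progression analysis: "it will be conducted at the patient level". The same section observes "Bilateral AMD disease is quite common (and will be identified") and defines one study eye per patient: "If patients are bilaterally diagnosed, the study eye will be selected at random".
- Section 9.7.1, progression objective: "Disease progression will be analyzed at both patient and each individual eye level". It adds "Bilateral GA eyes at baseline will be evaluated for progression to wAMD".
- Section 9.7.1, dry AMD to GA: the conversion analysis covers the "overall rate of dry AMD eyes developing GA, along with a Kaplan Meier analysis", so its unit is the eye.

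On methods, Section 9.6 reserves R for any statistical analysis "performed (t-tests, chi-square test or proportion, Confidence intervals etc". Section 9.7.1 adds Kaplan-Meier or Cox as options for progression. For comparing progression subgroups it names chi-squared tests or standardized mean differences, followed by logistic regression. No visible text mentions correlation between the eyes of a patient, GEE, mixed models, robust variance, frailty or a patient-level bootstrap. Section 9.6 also has the metrics leave the database in aggregated form before further analysis.

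**The concern.** Two eyes of one patient share age, smoking history, systemic disease and visit pattern, so their outcomes are likely to be positively correlated. A standard interval or test on pooled eyes counts each eye as a full independent observation. With positive correlation the interval is then too short and the test rejects too often.

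The proportional error depends on the share of paired eyes and on the correlation, and it does not shrink as the cohort grows. In a very large cohort the interval is so short that this hardly shows. In the smaller sets the plan intends to look at (patients with a documented lesion size, the longest follow-up, comorbidity groups) the interval width is something a reader would use.

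The conflict between Sections 9.1.1 and 9.7.1 adds to this, because a reader cannot tell which progression results will rest on one row per patient and which on one row per eye.

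**Working it through.** The plan states no interval width, standard error or significance level, so there is no figure of its own to reproduce.

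**Inputs from Section 9.5 (feasibility counts).** All GA: 72,718 patients, 113,408 eyes. With visits after 3 years: 20,503 patients, 31,647 eyes.

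**Assumed, not in the documents.** Between-eye correlation ρ of 0.3, 0.5 or 0.7, and a two-sided 95% level.

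**Step 1: share of paired eyes.** Each patient has one or two GA eyes, so two-eye patients = eyes − patients.

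- All GA: 113,408 − 72,718 = 40,690. Paired eyes = 81,380, and 81,380 / 113,408 = 71.8%.
- 3-year set: 31,647 − 20,503 = 11,144. Paired eyes = 22,288, and 22,288 / 31,647 = 70.4%.

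**Step 2: design effect for a pooled-eye proportion.** DEFF = 1 + fρ, where f is the share of paired eyes. Actual coverage of the naive interval = 2Φ(1.96/√DEFF) − 1. For all GA eyes (f = 0.718):

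| ρ | DEFF | SE ratio √DEFF | Coverage of nominal 95% CI | Actual error of a 5% test |
|---|---|---|---|---|
| 0.3 | 1.22 | 1.10 | 92.5% | 7.5% |
| 0.5 | 1.36 | 1.17 | 90.7% | 9.3% |
| 0.7 | 1.50 | 1.23 | 89.0% | 11.0% |

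In a set made up only of patients with both eyes included, such as the bilateral GA subgroup, f = 1 and DEFF = 1 + ρ. The error of a 5% test is then 8.6%, 11.0% or 13.3%.

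**Step 3: absolute size.** For a 20% proportion (an illustration, at the lower end of the conversion range in Section 7) and ρ = 0.5:

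- All GA eyes: 1.96 × √(0.16/113,408) = 0.23 percentage points. Multiplied by 1.17, this becomes 0.27.
- 3-year set: 1.96 × √(0.16/31,647) = 0.44 points. Multiplied by 1.16, this becomes 0.51.

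**Step 4: Kaplan-Meier.** A simulation used 1,119 two-eye and 881 one-eye patients, 20% events at 36 months, censoring shared within a patient, and 1,500 repetitions.

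| Latent correlation | Mean 36-month survival | True SE / Greenwood SE |
|---|---|---|
| 0 | 0.801 | 1.01 |
| 0.5 | 0.800 | 1.08 |
| 0.8 | 0.800 | 1.17 |

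The curve stays where it should; only its band is too narrow. Latent correlations of 0.5 and 0.8 correspond to correlations of about 0.29 and 0.56 between the 36-month event indicators. At those values the Step 2 formula gives √(1 + 0.718 × 0.29) = 1.10 and √(1 + 0.718 × 0.56) = 1.18, so the two approaches roughly agree.

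**Step 5: study eye against fellow eye.** For a contrast within patients, the true SE is √(1 − ρ) times the unpaired one: 0.84, 0.71 or 0.55 at ρ = 0.3, 0.5 or 0.7. Here ignoring the pairing makes intervals too wide.

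**The case against.** The strongest case on the other side is that this is largely a descriptive study. Most planned output is means, SDs, medians and counts. Tests and intervals appear in a parenthesis about software, Kaplan-Meier and Cox are optional, and silence on clustering is not a commitment to independence. Section 9.1.1 also takes one study eye per patient, at random where both are diagnosed together, which is a standard way to avoid the problem.

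Much of this stands. Analyses of study eyes alone, or fellow eyes alone, have one eye per patient and need no correction. It does not cover the eye-level progression analysis, the bilateral GA eyes if both are counted, or the dry AMD eye analysis. For those, the plan names ordinary methods and nothing else.

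Three stronger readings are tempting but are not supported:

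- **That the plan's error bars are already too narrow.** It states none. The shortfall arises only if the named methods are run on pooled eyes in their standard form.
- **That inflated p-values will drive variable selection for the logistic model.** Section 9.7.1 words those comparisons as groups of patients, and continuous variables are compared by standardized mean difference. Section 9.3.3.1 does record demographics at eye level, so stating the unit would help, but the text does not show that eye rows enter those tests.
- **That the 72% share applies to every eye-level analysis.** It describes GA eyes in the feasibility count. No matching patient count is given for dry AMD eyes, so the size of the effect on that Kaplan-Meier band cannot be derived.

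**Conclusion.** The concern holds in a limited form. The plan provides for eye-level analysis in Section 9.7.1, conflicts with Section 9.1.1 on the unit for progression, and names no way to handle paired eyes where eyes are pooled. For pooled GA-eye proportions, naive standard errors would be too small by a factor of about 1.10 to 1.23 over the assumed correlations of 0.3 to 0.7. The true correlation is unknown, and the pair share comes from feasibility counts that the plan says may change.

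No full-cohort descriptive conclusion is likely to change, since the shift there is a few hundredths of a percentage point. The point matters for p-values and intervals in small subsets, and because the choice is easiest to make before the data are extracted.

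**What to change.** 1. Reconcile Sections 9.1.1 and 9.7.1 by listing, for each analysis, whether the unit is the patient, the study eye, the fellow eye or pooled eyes.
2. Amend Section 9.6 so that the analysis file keeps eye-level rows with a de-identified patient ID. Clustering cannot be recovered from aggregates alone.
3. State that inference on pooled eyes is clustered on patient: GEE or sandwich variance for proportions and logistic models, Cox with robust variance by patient, and a patient-level bootstrap for Kaplan-Meier bands. Alternatively, limit inference to one eye per patient and leave pooled-eye results descriptive.
4. Treat any study-versus-fellow-eye contrast as paired.

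The cost is modest extra programming, more than a single option for the chi-square comparisons and the Kaplan-Meier bands, and intervals about 10% to 23% wider for pooled GA-eye proportions at correlations of 0.3 to 0.7. Kaplan-Meier estimates and simple proportions stay as planned.
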